7.6.2 Follow-up for toxicities

Patients whose treatment is interrupted or permanently discontinued due to a possibly study-drug related adverse event or abnormal laboratory value must be followed until resolution to CTCAE V 4.03 grade 2 or 30 days post last study drug administration, whichever comes first.

If a patient requires a dose delay of > 14 days from the intended day of the next scheduled dose, then the patient must be discontinued from the study. All patients will be followed for adverse events and serious adverse events for at least 4 weeks following the last dose of any study drug.

7.7 Other concomitant medications

Patients must be instructed not to take any additional medications (including over-the-counter products) during the trial without prior consultation with the investigator. All medications taken within 30 days of screening should be recorded. If concomitant therapy must be added or changed, the reason and name of the drug/therapy should be recorded.

In general, the use of any concomitant medication/therapies deemed necessary for the care of the patient are allowed, including IV bisphosphonates and drugs given prophylactically (e.g. antiemetics) with the following exceptions:

- Any medications listed in Section 19 which may cause QTc prolongation or inducing torsades de pointes should not be used.
- Any medications that have the potential to alter serum electrolytes (e.g., diuretics) should be monitored very closely for electrolyte abnormalities as these can contribute to the risk of QT prolongation and ventricular arrhythmias.
- No other investigational therapy should be given to patients
- No anticancer agents other than the study medications administered as part of this study protocol should be given to patients. If such agents are required for a patient then the patient must first be withdrawn from the study.
- Leukocyte growth factors (e.g. G-CSF and GM-CSF) are not to be administered systematically but may be prescribed by the investigator for severe neutropenia if this is thought to be appropriate, see also for guidance under table 7-4..
- Medications known to be substrates of the isoenzyme CYP2D6 should be used with caution with panobinostat as panobinostat can inhibit isoenzyme CYP2D6 at low micromolar ranges. Please refer to Section 21 for the list of CYP2D6 substrates. .
- Concomitant use of CYP3A4 inhibitors with panobinostat should be used with caution due to a potential increase in panobinostat exposure during concomitant treatment with these drugs.

- Oral contraceptives are generally metabolized by CYP3A4. Since the induction potential of panobinostat to induce CYP3A4 is unknown, patients who are using oral contraceptives as a method of contraception, and are sexually active, should use another effective contraceptive method.

7.7.1 Summary of commonly used allowed supportive concomitant medications

While a heightened awareness about possible pharmacokinetic and pharmacodynamic interactions should be maintained with any medication used concomitantly with study drugs the following are generally considered safe due to lack of reported interaction or large therapeutic window despite possible interaction:

- HT3 blockers (with caution, D/C if followed by QTcF prolongation), metoclopramide, and prochlorperazine
- Loperamide, diphenoxylate/atropine
- Azithromycin, levofloxacin, pefloxacin, ofloxacin, tosufloxacin, difloxacin, temafloxacin, fleroxacin, acrosoxacin, and nalidixic acid are allowed
- Acetaminophen and opioid analgesics other than methadone
- Regular orange juice and dihydropyridine calcium channel blockers (e.g. amlodipine, felodipine, nifedipine, nifedipine) are allowed
- IV bisphosphonates
- G-CSF, GM-CSF: Their use is allowed and should follow institutional practice and guidance outlined in table 7-4, alternative usage may be reviewed with Millennium and Novartis.
- Erythropoietin will be allowed in this study. Its use should follow published guidelines and/or institutional practice.
- Patients should be transfused with red cells and platelets as clinically indicated and according to institutional guidelines.
- Antiviral therapy such as acyclovir may be administered if medically appropriate.

7.7.2 Summary of prohibited concomitant medications and supplements

The following contains commonly used medications that should not be used during this study due to either pharmacokinetic interactions or pharmacodynamically based increased risk for adverse events. It is not inclusive. See Sections 19-21 for more information.

- Grapefruit or grapefruit juice and seville (sour) oranges (regular orange juice is allowed)

- Non-steroidal anti-inflammatory agents (NSAIDs) should be avoided if possible due to risk for kidney dysfunction in myeloma but if clinical judgement strongly argues for their use patients can remain on study while receiving NSAIDs
- Other antineoplastic agents
- Other investigational agents
- Aprepitant
- All Class IA antiarrhythmics: quinidine, procainamide, disopyramide, any other class IA antiarrhythmic drug
- All Class III antiarrhythmics: amiodarone, sotalol, bretylium, disopyramide, dofetilide, ibutilide, any other class III antiarrhythmic drug
- Calcium channel blockers: diltiazem, verapamil
- The following Antibiotics: Erythromycin, clarithromycin, telithromycin (azithromycin is allowed), enoxacin, sparfloxacin, ciprofloxacin, voriconazole, ketoconazole, and posaconazole
- Antipsychotics/antidepressants: thioridazine, mesoridazine, chlorpromazine, pimozide, fluvoxamine, nefazodone
- Antimalarials: halofantrine, chloroquine
- Miscellaneous drugs: arsenic trioxide, astemizole, bepridil, domperidone, levomethadyl, methadone, pentamidine, droperidol
- Strong inhibitors of CYP1A2: fluvoxamine, enoxacin, ciprofloxacin
- Strong inhibitors of CYP3A: clarithromycin, telithromycin, itraconazole, voriconazole, ketoconazole, nefazodone, and posaconazole
- Strong CYP3A inducers: rifampin, rifapentine, rifabutin, carbamazepine, phenytoin, and phenobarbital
- The dietary supplements St John's wort and Ginkgo biloba are not permitted.

The following procedures are prohibited during the study:

- Any antineoplastic treatment with activity against MM except for drugs in this treatment regimen.
- Radiation therapy (the requirement for local radiation therapy generally indicates disease progression). Platelet transfusions can be given as clinically indicated but eligibility for starting a new cycle needs to be determined after at least 72 h without platelet transfusion and eligibility for inclusion in this trial needs to be determined after at least 7 days without platelet transfusion. Adjuvant hormone therapy for breast or prostate cancer.

7.7.3 Anti-coagulant therapy

Panobinostat and MLN9708 therapy is commonly associated with mild to moderate degree of thrombocytopenia. This may lead to an increase in the risk of bleeding with concomitant sodium warfarin (Coumadin®). It is recommended that patients who require anticoagulation therapy while on panobinostat therapy use low molecular weight heparin (LMWH). However, if the use of LMWH is not feasible, patients on sodium warfarin may continue such therapy while on study but for such patients, a close and frequent monitoring of the coagulation parameters, including PT/INR should be followed and they should be maintained within a therapeutic range. The dose of sodium warfarin may be adjusted as needed while on study.

7.8 Precautions and Restrictions

- Fluid and electrolyte deficits should be corrected before and throughout treatment.
- Nonsteroidal anti-inflammatory drugs (NSAIDs) risk for nephrotoxicity is increased in patients with multiple myeloma, underlying kidney dysfunction, and dehydration. NSAIDs should generally be avoided in patients with multiple myeloma, especially if other risk factors co-exist.

7.9 Contraception Requirements

The effects of MLN9708 and panobinostat on human pregnancy or development of the embryo or fetus are unknown. Therefore, female patients participating in this study should avoid becoming pregnant, and male patients should avoid impregnating a female partner. Nonsterilized female patients of reproductive age and male patients should use effective methods of contraception through defined periods during and after study treatment as specified below.

Female patients must meet the following eligibility criteria:

- Are postmenopausal for at least 1 year before the screening visit, OR
- Are surgically sterile, OR
- Agree to practice true abstinence when this is in line with the preferred and usual lifestyle of the subject. (Periodic abstinence [e.g., calendar, ovulation, symptothermal, post-ovulation methods] and withdrawal are not acceptable methods of contraception.)
- Must also adhere to the guidelines of any treatment-specific pregnancy prevention program, if applicable, OR
- If they are of childbearing potential, agree to practice 2 effective methods of contraception, at the same time, for at least 28 days before starting study drug through 90 days after the last dose of study treatment.
 - The 2 methods of reliable contraception must include 1 highly effective method and 1 additional effective (barrier) method. Females of childbearing potential must be referred to a qualified provider of contraceptive methods if needed. The following are examples of highly effective and additional effective methods of contraception:

Highly effective methods:

- Intrauterine device (IUD)
- Hormonal (injections, implants)
- Tubal ligation
- Partner's vasectomy

Additional effective methods:

- Male condom
- Diaphragm
- Cervical Cap

Male patients, even if surgically sterilized (i.e., status post vasectomy), must meet the following eligibility criteria:

- Agree to practice true abstinence when this is in line with the preferred and usual lifestyle of the subject. (Periodic abstinence (e.g., calendar, ovulation, symptothermal, post-ovulation methods] and withdrawal are not acceptable methods of contraception.), OR
- Agree to practice effective barrier contraception during the entire study treatment period and through 4 months after the last dose of study treatment if their partner is of childbearing potential, even if they have had a successful vasectomy.
- Must also adhere to the guidelines of any treatment-specific pregnancy prevention program, if applicable.

7.9.1 CYP2D6 Substrates

In in vitro assays, panobinostat was shown to inhibit the cytochrome P450 isoenzyme CYP2D6 at low micromolar ranges, thereby suggesting a potential risk of drug-drug interactions with concomitant medications that are also metabolized by CYP2D6. A clinical drug-drug interaction study with dextromethorphan (a CYP2D6 probe drug) and panobinostat is currently ongoing in cancer patients. In the meantime, medications that are known to be CYP2D6 substrates should be used with caution when given concomitantly with panobinostat. Patients must be carefully monitored for signs of toxicity as a result of concomitant medication which may require dose titration or reduction of the CYP2D6 substrate as medically necessary. Please see Appendix 1 and refer to the following website: <http://medicine.iupui.edu/flockhart/table.htm> for a list of substrates of CYP2D6.

7.9.2 Drugs that can inhibit/induce CYP3A4/5

7.9.2.1 Drugs that can inhibit CYP3A4/5

Panobinostat is metabolized in vitro by CYP3A4/5. A clinical drug-drug interaction study with ketoconazole and panobinostat has recently been completed. The less than 2-fold increase in panobinostat AUC upon co-administration with ketoconazole suggests that CYP3A4 contribution to the total clearance of panobinostat is low. The observed interaction is not considered clinically relevant, as panobinostat doses at least 2-fold greater than 20 mg (40 and 60 mg) have been safely administered in patients. CYP3A4 inhibitors should have no major impact on the exposure of panobinostat and may be co-administered when medically necessary.

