7.9.2.2 Drugs that are potent CYP3A4/5 inducers

As it is with other medications that are metabolized by CYP3A4, clinical judgment is to be exercised when potent CYP3A4 inducers are concomitantly taken with panobinostat.

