Multiple ketoconazole doses at 400 mg increased C_{max} and AUC of panobinostat by 1.6- and 1.8-fold, respectively, but with no change in T_{max} or half-lives in 14 cancer patients. The less than 2-fold increase in panobinostat AUC upon co-administration of a strong CYP3A inhibitor is considered a weak drug inhibition and not clinically relevant, as panobinostat doses at least 2-fold greater than the evaluated 20 mg dose (i.e., 40 mg and 60 mg) have been safely administered in patients. Thus, co-administration of panobinostat with a moderate or weak CYP3A inhibitor is allowed. However, clinical monitoring of signs and symptoms of panobinostat treatment related adverse events is recommended when long-term (≥ 1 week) concomitant administration of any strong CYP3A inhibitors and panobinostat is medically indicated or investigated in a clinical study.

Patients with impaired liver function (as defined by NCI CTEP criteria)¹ are recommended not to receive panobinostat concomitantly with strong CYP3A inhibitors because potential interaction has not been established in this population.

Table 20-1 Medications which are known strong CYP3A4/5 inhibitors to be used with caution

Macrolide antibiotics*
 
 • clarithromycin • telithromycin • troleandomycin • erythromycin

Antifungals (azoles)*
 
 • ketoconazole • itraconazole • fluconazole

Antidepressants
 
 • nefazodone

Calcium channel blockers*
 
 • diltiazem • verapamil

HIV protease inhibitors:
 
 • indinavir • nelfinavir • ritonavir

 • saquinavir
Miscellaneous drugs or products 
 • aprepitant • grapefruit product or juice
* azithromycin, regular orange juice and dihydropyridine calcium channel blockers (e.g. amlodipine, felodipine, nicardipine, nifedipine) are allowed.

This is not a comprehensive list of medications which may inhibit CYP3A4/5. Additional updated versions with moderate and weak CYP3A inhibitors, which are meant to be used as a guide, may be found at the following website: <http://medicine.iupui.edu/clinpharm/DDIs>

21 Medications which are known CYP2D6 substrates to be used with caution

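### Section 7.7.2 bars named CYP3A inhibitors and strong inducers, but 7.9.2 and Table 20-1 leave room to use some of them, and no text says which rule governs

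*Combined protocol and SAP*

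**What the plan says.** Section 7.7.2, which is headed as a list of prohibited medications, covers "commonly used medications that should not be used during this study". Its entries include "Strong inhibitors of CYP3A: clarithromycin, telithromycin, itraconazole, voriconazole, ketoconazole, nefazodone, and posaconazole" and "Strong CYP3A inducers: rifampin, rifapentine, rifabutin, carbamazepine, phenytoin, and phenobarbital". Other bullets in the same list name erythromycin, diltiazem, verapamil, aprepitant and grapefruit. The section calls its list non-exhaustive and points the reader to Sections 19 to 21.

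Other current sections read differently:

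- Section 7.9.2.1: "CYP3A4 inhibitors should have no major impact on the exposure of panobinostat and may be co-administered when medically necessary".
- Section 7.7: "Concomitant use of CYP3A4 inhibitors with panobinostat should be used with caution".
- Section 7.9.2.2: "clinical judgment is to be exercised when potent CYP3A4 inducers are concomitantly taken with panobinostat".
- Section 20 allows weak and moderate inhibitors. It recommends clinical monitoring when long-term (a week or more) "concomitant administration of any strong CYP3A inhibitors and panobinostat is medically indicated or investigated in a clinical study". Only patients with impaired liver function "are recommended not to receive panobinostat concomitantly with strong CYP3A inhibitors".
- Table 20-1 lists 16 entries as strong inhibitors for cautious use, and Section 19 repeats that advice. Section 19 also tells the reader to take the strictest advice for a drug that appears in more than one of the appendix tables.

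**The concern.** These are operative instructions to treating physicians, and for some drugs they point in different directions. Ketoconazole is the clearest case. Section 7.9.2.1 bases its permission on a ketoconazole interaction study, while 7.7.2 bars ketoconazole twice, in its antibiotics bullet and in its strong-inhibitor bullet.

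The permission in 7.9.2.1 is argued from panobinostat exposure alone. Both dose levels in Section 5.3 also include ixazomib. Sections 1.3.3 and 1.3.7 say that ixazomib may interact with strong CYP3A inhibitors, and 1.3.3 adds strong inducers. A physician who relies on 7.9.2.1 is therefore relying on an argument that omits one of the two investigational drugs. Phase II treatment has no fixed end (Section 5.2), so the question can recur over many cycles.

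There is also a conduct issue. If one site follows 7.7.2 and another follows 7.9.2.1, the protocol does not settle whether the second has deviated.

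**Working it through.** The plan gives no figure on this point, so the check is a comparison of texts and lists.

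**1. The rules side by side**

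| Place | CYP3A inhibitors | Strong CYP3A inducers |
|---|---|---|
| 7.7.2 | Named drugs not to be used | Six named drugs not to be used |
| 7.7 | Caution, listed as an exception to the general allowance | No rule |
| 7.9.2.1 | May be given when needed, any strength | No rule |
| 7.9.2.2 | No rule | Clinical judgment |
| 19 and 20, Table 20-1 | Cautious use; monitoring for prolonged use of strong ones | No rule |
| Exclusion 16 | Named strong ones barred for 14 days before enrollment | The same six barred for 14 days before enrollment |

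**2. Entries in Table 20-1:** 4 macrolides + 3 azoles + 1 antidepressant + 2 calcium channel blockers + 4 HIV protease inhibitors + 2 miscellaneous = 16.

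**3. Entries also named in 7.7.2:** five in its strong-inhibitor bullet (clarithromycin, telithromycin, itraconazole, ketoconazole, nefazodone) and five elsewhere in the list (erythromycin, diltiazem, verapamil, aprepitant, grapefruit). 5 + 5 = 10.

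**4. Entries for which some other text also gives a bar:** erythromycin, clarithromycin and telithromycin are also in Table 19-1, so the Section 19 rule sends them to avoidance (3). Section 7.1.1 bars grapefruit outright (1).

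**5. Remainder:** 10 - 3 - 1 = 6, namely ketoconazole, itraconazole, nefazodone, diltiazem, verapamil and aprepitant. For these, 7.7.2 is the only bar during treatment, and Table 20-1 names the same drugs for cautious use.

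**6. Entries not named in 7.7.2:** 16 - 10 = 6, namely troleandomycin, fluconazole, indinavir, nelfinavir, ritonavir and saquinavir. These do not contradict 7.7.2.

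**7. Does any text settle the order of precedence?** The Section 19 rule works among the appendix tables and does not mention 7.7.2 or 7.9.2. Section 7.7.2 claims no priority, and its cross-reference leads to the cautious-use advice. Exclusion 16 stops at enrollment and, of the six drugs in step 5, names only ketoconazole, itraconazole and nefazodone. Section 7.7 requires consultation with the investigator before any added drug, but the investigator reads the same texts. Section 7.6 asks for interactions with both study drugs to be weighed when other antibiotics are chosen for mild infections, and it does not rank the sections either.

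**The case against.** The best defense is that the texts can be read together. Sections 7.7 (the CYP3A4 line), 7.9.2.1, 7.9.2.2 and 20 speak of panobinostat, whereas 7.7.2 speaks for the whole study. A named prohibition normally limits a general permission, and obeying 7.7.2 breaches no other section. The last point stands: a reader might infer two rules that cannot both be obeyed, and that is too strong. The rest does not close the gap. The protocol never says that the looser sections cover panobinostat alone, and Table 20-1 names the six drugs as specifically as 7.7.2 does.

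Four other stronger readings are tempting and are not supported:

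- *That 7.7 authorizes CYP3A4 inhibitors.* Its line is one of the exceptions to a general allowance, so it restricts use.
- *That the inducer mismatch is as sharp as the inhibitor one.* Asking for clinical judgment does not authorize the drugs. It does, however, presuppose that drugs barred in 7.7.2 might be taken.
- *That aprepitant, diltiazem or verapamil would cause an ixazomib interaction.* The warnings in 1.3.3 and 1.3.7 concern strong inhibitors. Section 7.7.2 places these three outside its strong-inhibitor bullet, and only the appendix calls them strong. For nausea, 7.7.1 already offers alternatives.
- *That all 16 Table 20-1 entries should be barred.* For the six entries in step 6 that would be a new clinical restriction, not the removal of a contradiction. The HIV protease inhibitors matter little in practice, because exclusion 17 removes patients known to be HIV positive.

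The count of six can also be challenged, because it credits the Section 19 rule and 7.1.1 with resolving four entries. Without that credit the overlap is ten. Nor does the Section 19 rule settle 7.9.2.1 against 7.7.2. The finding itself does not depend on which count is used.

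**Conclusion.** The inconsistency holds and is minor. Section 7.9.2.1, and Table 20-1 with Sections 19 and 20, are looser than 7.7.2 for drugs that 7.7.2 bars by name. Six Table 20-1 drugs are affected with no other bar during treatment. Section 7.9.2.2 is more mildly out of step for six named inducers.

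This rests on two readings: that 7.7.2 is meant as a prohibition, as its heading says, and that the Section 19 rule is confined to the appendix tables, as its wording indicates. No harm is quantified, and the documents do not allow it to be. The stricter rule is already in the protocol, and no endpoint, analysis or sample-size figure changes.

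**What to change.** 1. Replace the last sentence of 7.9.2.1 with: *CYP3A inhibitors named in 7.7.2, including the strong inhibitors, are prohibited during study treatment; other CYP3A inhibitors may be used with caution and with monitoring for panobinostat and ixazomib toxicity.* In 7.7, add to the CYP3A4 line: *except those prohibited in 7.7.2*.
2. In 7.9.2.2, state that strong CYP3A inducers are prohibited as listed in 7.7.2.
3. In Sections 19 and 20, state that 7.7.2 prevails for any Table 20-1 drug that it names, and mark those ten entries as prohibited. Leave troleandomycin, fluconazole and the four HIV protease inhibitors for the sponsor to classify.

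The cost is a wording amendment, with no new data or procedures. Under Section 11 it needs review by both drug suppliers and the sponsor-investigator, and IRB approval if it is judged to affect subject safety significantly.

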7.9.2.2 Drugs that are potent CYP3A4/5 inducers

As it is with other medications that are metabolized by CYP3A4, clinical judgment is to be exercised when potent CYP3A4 inducers are concomitantly taken with panobinostat.

7.10 Treatment compliance

Records of study medication used, dosages administered, and intervals between visits will be recorded during the study. Drug accountability will be noted and patients will be asked to return all unused study medication.

8 Visit schedule and assessments

Table 8-1 Schedule of Assessments*

Examinations	Screening	Cycle 1			Cycles 2 and beyond		Study exit ⁸
	D-7 to D1	D1	D5	Weekly	D 1	Weekly	
Informed consent	X						
Background information ¹	X						
Inclusion/exclusion criteria	X						
Bone marrow examination ₂	X						
Skeletal survey ³	X						
Echocardiogram or MUGA scan ³	X						
Vital signs ⁴		X		X	X		X
History & Physical examination	X	X		X	X		X
ECG ⁵	X	X	X		X ⁵		
CBC/Diff	X	X		X	X	X ¹⁰	X
PTT, INR	X						
CMP,, magnesium	X	X		X	X	X ¹⁰	X
Response parameters SPEP, 24h UPEP, sFLCs, serum and urine IFE	X				X		X
TSH, free T3, FTI	x				Cycle 4X ⁹		X
Pregnancy testing ⁶	X				X		
Compliance review/drug calendar ⁷					X		X

* Unless noted otherwise all visits and assessments should occur on the scheduled day +/- 3 days but a new cycle may not begin unless ECG and electrolyte assessment has been completed within 24h prior to day one dosing and criteria are met for the start of a new cycle (7.4).

1) Background information. The treating physician is responsible for comprehensive assessment of background information as it relates to eligibility for this trial. The following will be recorded on the CRFs: Year and month symptomatic myeloma was diagnosed, cytogenetic findings at diagnosis (karyotype, FISH, gene expression profile as available), beta 2 microglobulin, serum albumin, and LDH levels at diagnosis, number of prior therapies, and responses to prior therapies. Past medical history, past surgical history, and allergies as recorded in patient's charts 6 month prior to enrollment and all concomitant medications at the time of enrollment will also be recorded.

2) Bone marrow examinations: In general this will only be done once at screening or within 28 days prior to study entry but for patients who appear to have reached a complete remission based on blood and urine studies it will be repeated for confirmation. Patients who have measurable disease only in the bone marrow will have bone marrow examinations after cycle 2 and at the end of the study. Additional bone marrow examinations may be obtained as clinically indicated. 3) Skeletal survey and left ventricular ejection fraction determination by Echocardiogram or MUGA scan: Within 28 days prior to study entry.

4) Vital sign assessment consists of height (first visit), pulse, blood pressure, respiration rate, temperature and weight. Blood pressure, pulse and respiration rate should be measured on patients after at least 3 minutes in the sitting position

5) ECGs:

- On Screening: One ECG
- On day 1 and 5 of cycle 1: Pre-dose: One ECG, Post-dose at 3 hours \pm 0.5 hour: One ECG
- On day 1 of cycle 2: Pre-dose: One ECG
- Additional ECGs as detailed under 7.5.4 may be necessary if QTcF prolongation prevents dosing of panobinostat and MLN9708 or if felt clinically necessary for other reasons

6) Pregnancy tests for females of childbearing potential. A female of childbearing potential (FCBP) is a sexually mature female who: 1) has not undergone a hysterectomy or bilateral oophorectomy; or 2) has not been naturally postmenopausal for at least 24 consecutive months (i.e., has had menses at any time in the preceding 24 consecutive months). All females of childbearing potential should complete a serum pregnancy test within 7 days prior to the administration of study drugs on day 1 of cycle 1. The pregnancy test should be repeated in week 1 of every cycle (except for cycle 1).

7) Compliance review / study calendar: Nurses review medication compliance based on study calendar patients fill out.

8) Study exit: Visits and assessments at study exit should occur within 3 days prior and 7 days after the end of the previous cycle or within 7 days after the decision to remove the patient from study. If grade \geq 3 non-hematologic adverse events or grade 4 neutropenia or thrombocytopenia are present at study exit, the respective adverse events should be followed weekly until resolution to grade 2 for non-hematologic adverse events and grade 3 for neutropenia and thrombocytopenia or until 30 days from last treatment have elapsed.

9) Thyroid function tests should be obtained at study entry, at about 3 months from study entry, ideally after the third 28-day cycle, whenever there is clinical suspicion for hypothyroidism, and at the completion of this study unless it has been obtained within 30 days prior to study exit.

10) Weekly CBC/diff, CMP, and magnesium until completion of cycle 2, then as clinically indicated

